7.6.3 Primary Efficacy Analysis

The primary efficacy endpoint is mean change in the weekly number of UI episodes from study baseline to Week 6 after the first treatment. Seven-day bladder diaries that contain data recorded on at least 5 days will be included in the analysis.

As all subjects should have visits up to and including week 12, but thereafter visits are dependent on whether the subject receives retreatment, statistical testing between treatment groups will be performed only up to Week 12, inclusive. Descriptive statistics table will present any timepoint.

Weekly number of UI episodes and the mean change from study baseline will be presented for the DBPC Cycle. The mixed model repeated measures (MMRM) analysis will be conducted with the change of the weekly number of UI episodes from study baseline as response variable. Fixed effect variables include treatment group, visit (Week 2, Week 6 and Week 12), treatment-by-visit interaction, stratification variables [the aetiology of NDO and prior intradetrusor BTX-A usage for UI] and study baseline value of weekly number of UI episodes. Random effect will include the subject effect. An unstructured covariance matrix will be specified in the mixed

model to account for within subject correlation. If model fails to converge, the structure of first order autoregressive AR (1), compound symmetry (CS) or variance components (VC) will be used.

The least square means (LSMEANS) of the change of weekly number of UI at each visit in each group with standard error, the difference of mean between the two treatment groups at each visit, the 95% CI of the difference and the p-value for treatment group will be presented. The comparison of main interest will be treatment difference at Week 6.

The SAS codes of MMRM for reference are below.

```
CCI  
[Redacted SAS code for MMRM]
```

The validity of the model assumptions of normality will be investigated using residual plots. The LS means of change from study baseline for weekly UI in the DBPC and Dysport Cycles will be presented in line plots by treatment groups.

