2.3 Sample Size and Power

The sample size is based on the ability to detect a statistically significant treatment difference in the weekly number of UI episodes at Week 6 following the first IMP administration in the two Dysport arms (600 U and 800 U) compared to the placebo arm.

Assuming a weekly decrease of 21 UI episodes in each Dysport arm and a weekly decrease of 12 UI episodes in the placebo arm, with a common standard deviation of 20 UI episodes, 80% power, and an alpha of 0.025 (as testing of both the 600 U and 800 U doses vs. the placebo dose will be performed simultaneously), a sample size of 96 subjects per dose group (a total of 288 subjects) is needed. Dropout between randomisation and Week 6 (primary efficacy timepoint) is expected to be 10%, and thus a total of 318 subjects would be needed to be enrolled. However, in order to ensure that the development program will deliver adequate Dysport exposure data to meet ICH E1 guideline recommendations, a total of 330 subjects are planned to be randomised. Subjects who leave the study early will not be replaced.

Sample size calculations were performed in SAS Studio 3.6.

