7.6.4.2 Using ANCOVA

The analysis of covariance (ANCOVA) will be conducted for the two primary tests (Dysport 600 U vs. placebo, and Dysport 800 U vs. placebo), with the change of the weekly number of UI episodes from study baseline as response variable, including treatment group, stratification variables [the aetiology of NDO (SCI or MS) and prior intradetrusor BTX-A usage for UI (BTX-naïve or BTX-non-naïve)] and study baseline value of weekly number of UI episodes as covariates.

The least square means (LSMEANS) of the change of weekly number of UI at Week 6 in each group with standard error, the difference of mean between the treatment groups, the 95% CI of the difference and the p-value for treatment group will be presented.

The SAS codes of ANCOVA for reference are below.

```
CCI  
[Redacted SAS code for ANCOVA]
```

CCI [redacted]
[redacted]
[redacted]
[redacted]
[redacted]
[redacted]
[redacted]
[redacted]

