7.6.5 Hierarchical Analysis of Secondary Efficacy Endpoints

As specified in Section 7.6.12, a hierarchical analysis will be performed in the order listed for the following six secondary efficacy endpoints at Week 6 after the first IMP administration:

- 1) Mean change from study Baseline in the MCC
- 2) Mean change from study Baseline in the MDP during storage
- 3) Mean change from study Baseline in the Vol@1stIDC
- 4) Proportion of subjects with no episodes of UI (i.e. continence is achieved)
- 5) Proportion of subjects with no IDCs during storage
- 6) Mean change from study Baseline in the I-QoL total summary score

The Derivation rules are specified in Section 3.2 and Appendix II.

For 1), 2) and 3), an ANCOVA model will be fitted using the “mean change” endpoint, as the response variable to obtain the p-value of treatment groups. The model will be the same as the sensitivity analyses for the primary efficacy endpoint in 7.6.4.2. The LSMEANS of the mean change from study baseline at Week 6 in each group with standard error, the difference of mean between the two treatment groups, the 95% CI of the difference and the p-value for treatment group will be presented.

For 4), a logistic generalised linear mixed model (GLMM) for repeated measures will be fitted for UI responses using repeated measurements at Week 2, Week 6, and Week 12. The “proportion of subjects with no episodes of UI” will be analysed as a response variable, the model will include treatment group, stratification variables, study baseline value, visit (week 2, week 6 and week 12), study baseline*visit and treatment*visit interactions as fixed effect. The study baseline value will be weekly number of UI episodes. The logistic GLMM is fitted using the logit link and the binomial distribution. Odds ratios, 95% CIs of odds ratio, and p-values for treatment group comparisons at each visit (week 2, week 6 and week 12) will be presented.

The SAS codes of GLMM for reference are below.

```
CCI
[Redacted SAS code]
```

CCI
[Redacted]
[Redacted]
[Redacted]

For 5), a logistic regression model will be performed with “proportion of subjects” as the response variable. The model will include treatment group, and stratification variables.

Odds ratio, 95% CI of odds ratio, and p-value will be presented.

The SAS codes of logistic regression for reference are below.

CCI
[Redacted]
[Redacted]
[Redacted]
[Redacted]
[Redacted]
[Redacted]
[Redacted]
[Redacted]

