For 6), MMRM model will be fitted using the “mean change” endpoint, as the response variable to obtain the p-value of treatment groups. The model will be the same as primary analysis model in section 7.6.3. The least square means of change at Week 6 in each group with standard error, the mean difference of pairwise comparison, the 95% CI of the difference and the p-value for the treatment groups will be presented for each model.

If the testing procedure is stopped at the end of any particular step, the outcomes of the following steps will be presented and used for description only and no formal statistical conclusion will be drawn.

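### The primary repeated-measures model uses one baseline slope for Weeks 2, 6 and 12; adding baseline-by-visit would protect the Week 6 contrast at negligible cost, with a gain that is probably small

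*SAP*

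**What the plan says.** SAP 7.6.3 models the change from baseline in weekly episodes at Weeks 2, 6 and 12. The list of terms begins "Fixed effect variables include treatment group, visit (Week 2, Week 6 and Week 12), treatment-by-visit interaction, stratification variables" and closes "and study baseline value of weekly number of UI episodes. Random effect will include the subject effect". On covariance it says "An unstructured covariance matrix will be specified in the mixed" model, with AR(1), compound symmetry or variance components as fallbacks if the model does not converge. Week 6 is named as the comparison of main interest.

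Three other places bear on the point:

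- SAP 7.6.5, item 4 (continence): the logistic repeated-measures model at the same three visits lists "study baseline*visit and treatment*visit interactions as fixed effect", with baseline weekly episodes as the baseline variable.
- SAP 7.6.5, item 6 (I-QoL): "The model will be the same as primary analysis model in section 7.6.3".
- SAP 7.6.4.2: an ANCOVA sensitivity analysis reports "The least square means (LSMEANS) of the change of weekly number of UI at Week 6 in each group with standard error". It uses Week 6 data only, so it estimates its own Week 6 slope.

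The protocol synopsis asks only for treatment group, stratification variables and baseline value, so a further baseline term would not conflict with it. The reference code in 7.6.3 is redacted; the point rests on the SAP text.

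**The concern.** Change in weekly episodes must depend on baseline, because nobody can lose more episodes than they started with. If the reduction is roughly proportional to baseline, the slope follows the size of the effect, and the size of the effect may differ between Weeks 2, 6 and 12. A model with one slope then adjusts the Week 6 comparison with a value partly set by the other two visits.

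Two things would follow. Some variance that baseline could explain stays in the Week 6 contrast, so its standard error is a little larger than it need be. And if the arms differ at baseline by chance, the adjustment removes only part of that difference. Week 6 is the primary timepoint, and the SAP gives no reason for treating baseline differently in the primary model and the continence model.

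**Working it through.** **1. The plan's own figure.** SAP 2.3 takes mean weekly reductions of 21 episodes on active treatment and 12 on placebo. Its other inputs are "with a common standard deviation of 20 UI episodes, 80% power, and an alpha of 0.025". The difference is 21 − 12 = 9. By the normal approximation, n per group = 2 × (2.2414 + 0.8416)² × 20² / 9² = 93.9, so 94; the noncentral t gives 96, the stated figure. The plan relies on an unadjusted standard deviation of 20 and counts on no gain from baseline adjustment.

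**2. Effect of a common slope.** Let b be the true slopes at the three visits, b6 the Week 6 slope and S the residual covariance matrix, with S66 its Week 6 variance. In large samples:

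- the common slope tends to b* = (1′S⁻¹b) / (1′S⁻¹1), which is the simple mean of the slopes when visit variances and correlations are equal;
- the Week 6 contrast equals the difference in mean change minus b* times the difference in mean baseline;
- its variance is therefore larger by the factor R = 1 + Var(baseline) × (b6 − b*)² / S66.

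**3. Inputs.** From the documents: a difference of 9, a total standard deviation of 20, alpha 0.025 two-sided, and 110 per arm less 10% dropout = 99 per arm. Assumed, because the documents give none: baseline standard deviation 15 to 20, Week 6 slope −0.6, and correlation 0.5 to 0.8.

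S66 = 20² − 0.6² × Var(baseline):

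- baseline SD 15: 400 − 0.36 × 225 = 319, residual SD 17.86;
- baseline SD 20: 400 − 0.36 × 400 = 256, residual SD 16.

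Power = Φ(9 / (SD × √(2/99)) − 2.2414), which is 0.904 and 0.957 respectively with the correct Week 6 slope.

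**4. Results, equal visit variances and equal correlations** (left figure for baseline SD 15, right for 20):

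| Slopes, Weeks 2 / 6 / 12 | b* | Gap | R | Standard error without the term | Power lost (points) |
|---|---|---|---|---|---|
| −0.60 / −0.60 / −0.60 | −0.600 | 0 | 1 | no change | 0 |
| −0.55 / −0.60 / −0.50 | −0.550 | 0.050 | 1.002, 1.004 | +0.1%, +0.2% | under 0.1 |
| −0.40 / −0.60 / −0.40 | −0.467 | 0.133 | 1.013, 1.028 | +0.6%, +1.4% | 0.4, 0.5 |
| −0.20 / −0.60 / −0.20 | −0.333 | 0.267 | 1.050, 1.111 | +2.5%, +5.4% | 1.6, 2.2 |

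Example for row 3, baseline SD 20: R = 1 + 400 × 0.133² / 256 = 1.028, whose square root is 1.014.

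With unequal visit standard deviations or AR(1) correlation at baseline SD 20, the largest losses in rows 2, 3 and 4 were 0.8%, 3.4% and 13% in standard error, or 0.3, 1.3 and 6 points of power. Some unequal-variance patterns made the loss smaller than in the table.

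**5. Simulation check** (110 per arm, 10% missing at Week 6, skewed baseline, unstructured covariance, 800 trials per setting). The variance ratio, common slope to visit-specific slopes, was 1.000 to 1.001 for row 1, 1.009 to 1.026 for row 3 and 1.06 to 1.12 for row 4. Mean bias of the Week 6 contrast was at most 0.09 episodes under both models, within simulation error.

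**6. Chance imbalance.** The standard error of the baseline difference is 15 × √(2/99) = 2.1 to 20 × √(2/99) = 2.8 episodes. In row 3, an imbalance of one standard error leaves 0.133 × 2.1 = 0.3 to 0.133 × 2.8 = 0.4 episodes uncorrected, against a target of 9.

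**7. Cost of the term.** Two more parameters raise the t critical value by a factor of about 1.00004 (290 against 292 degrees of freedom). With parallel slopes the model standard error is about 0.1% larger with the term.

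**The case against.** The strongest reply is that the gain is conditional and nothing essential is at risk. Every magnitude above depends on assumed slopes. The documents do not show the effect waning by Week 12: protocol 1.3.2 reports reductions of 76% and 88% at 12 weeks in phase IIa, and protocol 1.4 says the maximum was seen as early as Week 6. If the Week 12 slope equals the Week 6 slope, the loss shrinks. With baseline SD 18 and residual SD 16, slopes of −0.6/−0.7/−0.7 give R = 1 + 324 × 0.0333² / 256 = 1.0014, and even −0.4/−0.8/−0.8 gives 1 + 324 × 0.1333² / 256 = 1.023, about 1.1% in standard error. The Week 6 ANCOVA is already prespecified, so a material difference in slopes should show there. The continence model is on a logit scale, and a term in it does not oblige the primary model to carry the same one.

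Most of this stands, and it limits the size of the point. It does not remove it: the ANCOVA is only a sensitivity analysis, and no other text supplies the term for the primary model.

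A reader might infer three stronger things that the documents do not support:

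- **That the primary comparison is biased or its type I error inflated.** Randomisation protects both; the residual error is conditional on the imbalance that happens to occur.
- **That the term is certain to improve precision.** With parallel slopes it does not.
- **That the amended model would reproduce the Week 6 ANCOVA.** It would be close, not equal, because the stratification effects stay common across visits. In 200 simulated complete-data trials the two differed by 0.07 episodes on average and by up to 0.45; they coincided only when strata-by-visit terms were added as well.

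**Conclusion.** The point holds as a minor improvement, not as an error in the plan. As written, the primary model fits one baseline slope across three visits, while a companion model on the same diary data lets the slope vary. The likely benefit of the extra term is between nothing and about 1.4% in the Week 6 standard error, or up to about 0.5 percentage point of power. This range assumes baseline SD 15 to 20, a Week 6 slope near −0.6, slopes at the other visits within about 0.2 of it, and equal visit variances and correlations. Larger benefits need strongly different slopes, unequal visit variances or AR(1)-type correlation, and the documents give no evidence for or against these. Because the sample size assumes no gain from baseline adjustment, the planned 80% power does not depend on this choice. The case for the change is that the protection costs almost nothing.

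**What to change.** Before database lock and unblinding, add a study baseline-by-visit interaction to the fixed effects in SAP 7.6.3. Then state which other models take it:

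- **Include:** the I-QoL model (7.6.5 item 6 and 7.6.6.3), the Week 2 and Week 12 weekly-episode analyses (7.6.6.1.1), EQ-5D-5L (7.6.6.3), and urinary frequency and voided volume (7.6.6.1.2).
- **Correct a cross-reference:** 7.6.6.1.2 calls for the repeated-measures model but points to 7.6.4.2, the ANCOVA section; it should point to 7.6.3. Without this the change does not carry over.
- **Leave out:** the urodynamic endpoints, which have a single post-baseline visit, and mPGI-I, which has no baseline.

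If the sponsor prefers to keep the common slope, one sentence saying why the primary model differs from the continence model would do. The cost is a one-phrase SAP amendment and two fixed-effect parameters in the three-visit models (one where only Weeks 6 and 12 are analysed). This is a negligible cost rather than none, since it changes the primary model in a finalised SAP. The protocol needs no change.

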For continuous endpoints analysed by mean or mean change values, inference will be done using mixed-models repeated measures, which assumes that missing outcomes are missing at random (MAR).

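### The convergence fallback for the primary model is unordered and assumes equal variance at every visit, so if it is used the Week 6 standard error can be wrong in either direction; the random subject effect beside the unstructured matrix is redundant and should go

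*SAP*

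**What the plan says.** SAP 7.6.3 fits a mixed model to change from baseline in weekly incontinence episodes, with fixed effects that include "visit (Week 2, Week 6 and Week 12), treatment-by-visit interaction". On the covariance it says "Random effect will include the subject effect. An unstructured covariance matrix will be specified" in the mixed model, to account for within-subject correlation. The contingency reads: "If model fails to converge, the structure of first order autoregressive AR (1), compound symmetry (CS) or variance components (VC) will be used". The target is stated plainly: "The comparison of main interest will be treatment difference at Week 6".

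The visible text gives no order among the three structures, no selection criterion, no heterogeneous versions and no robust standard error. The only model check named is normality, by residual plots. The reference SAS code is redacted. The protocol synopsis says only that a mixed model with treatment, stratification variables and baseline will be used. SAP 7.6.4.2 adds a Week 6 ANCOVA as a sensitivity analysis, and SAP 6.2.1.1 rests the repeated-measures inference on data missing at random.

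**The concern.** Two things look wrong. First, an unstructured matrix over three visits already uses every variance and covariance available, so a random subject intercept has nothing left to estimate. A fit of that model may report a convergence or Hessian problem, and that is the event that activates the fallback.

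Second, the fallback changes the variance used for the primary test. Under AR(1), compound symmetry or variance components, the Week 6 contrast takes its standard error from a variance pooled over Weeks 2, 6 and 12. AR(1) also treats the 4-week and 6-week gaps as equal. With no order stated, the choice among three structures falls after the fit has been seen.

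This test opens the Hochberg procedure and the six-endpoint hierarchy (SAP 7.6.2), whose error control assumes a valid Week 6 standard error. The same model serves the sixth hierarchical endpoint (SAP 7.6.5), the per-protocol analysis (7.6.4.1) and the mis-stratification analysis (7.6.4.4), so those do not act as independent checks.

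**Working it through.** **Inputs from the documents.** Three visits in the model (SAP 7.6.3). Difference 21 − 12 = 9 episodes per week, SD 20, 80% power, alpha 0.025 per comparison, 96 evaluable per group, 10% dropout, 330 randomised (SAP 2.3). Two-sided tests (protocol 9.3).

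**Assumptions.** Residual SDs at Weeks 2 and 12, and a within-subject correlation of 0.6 in the simulations. The documents give one SD, 20, for Week 6.

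**The plan's own figure.** The normal approximation for difference 9, SD 20, alpha 0.025 and 80% power gives 94 per group. The t-based solution is 95.1, so 96, with power 80.4%. The stated 96 is reproduced. The corresponding Week 6 standard error is 20 × √(2/96) = 2.887.

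**Identifiability.** A 3×3 covariance has 3 variances + 3 covariances = 6 distinct elements. Unstructured plus random intercept has 7 parameters; the Jacobian of the 6 elements with respect to them has rank 6. Compound symmetry plus intercept is also redundant (3 parameters, rank 2). AR(1) plus intercept (3 of 3) and variance components plus intercept (2 of 2) are identified.

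**Does the redundancy alter the result?** In one simulated data set (110 per arm, 10% dropout after Week 2), moving 0, 50, 100 or 150 of variance from the unstructured part to the intercept left −2 REML log-likelihood at 6107.77 and the Week 6 standard error at 2.869 each time. It does not.

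**Does the fallback alter it?** With roughly equal numbers at each visit:

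- pooled SD = √(mean of the three squared SDs)
- ratio = pooled SD / Week 6 SD
- actual type I error per comparison = 2 × (1 − Φ(z × ratio)), with z = 1.96 at nominal 5% and 2.24 at nominal 2.5%

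For 16/20/18: √((256 + 400 + 324)/3) = 18.07; ratio 18.07/20 = 0.904; 2 × (1 − Φ(1.771)) = 7.7%.

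| Assumed SDs, Weeks 2/6/12 | Pooled SD | Ratio | Type I at 5% | Type I at 2.5% |
|---|---|---|---|---|
| 16/20/16 | 17.44 | 0.872 | 8.8% | 5.1% |
| 16/20/18 | 18.07 | 0.904 | 7.7% | 4.3% |
| 18/20/22 | 20.07 | 1.003 | 4.9% | 2.5% |
| 18/20/24 | 20.82 | 1.041 | 4.1% | 2.0% |
| 25/20/25 | 23.45 | 1.173 | 2.1% | 0.9% |

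In the last row, power at alpha 0.025 falls from 81% to 69%.

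**Simulation check** (400 trials per scenario, Monte Carlo error about 0.01 on rejection rates, nominal 0.05). For 16/20/16 the unstructured fit rejected 0.054, and AR(1), compound symmetry and variance components 0.094, 0.091 and 0.092. For 25/20/25 the rates were 0.036, 0.010, 0.010 and 0.016. For 20/20/20 all four were about 0.05.

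**Missing data.** With Week 6 missingness driven by Week 2 (14% against 10% missing, correlation 0.7) and a true difference of −9, complete-case contrasts in similar set-ups came to −8.4 to −8.6. Variance components with no subject effect would behave this way. Variance components with a random subject effect, which is compound symmetry, gave −8.9 to −9.0.

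**The case against.** The best defence is that the sentence about the subject effect may simply identify the clustering unit. SAP 7.6.3 calls the model MMRM and gives the unstructured matrix the job of handling within-subject correlation. The redacted code would settle the matter and cannot be held against the plan. On that reading nothing is over-parameterised, and the fallback is remote: with 330 subjects, three visits and 10% dropout, an unstructured model alone converged in 300 of 300 simulated trials. No failed fit of the redundant model has been shown either. This stands, and it limits how likely the problem is.

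It can also be said that the concern must not combine two readings. If a random subject effect is really fitted, it stays in the fallback, and variance components then keeps the within-subject correlation. This also stands. A reader might infer that the plan loses its missing-at-random basis. The documents do not support that in general: it would apply only to variance components with no subject effect. In that illustration the bias was also towards zero, with none of note under the null (0.03).

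The equal-variance point survives either reading, because adding a subject intercept to AR(1) or variance components still leaves one common variance across visits.

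Finally, the Week 6 ANCOVA uses only Week 6 variance, and multiple imputation is planned for missing data. Both are useful, but as sensitivity analyses neither replaces the primary p-value.

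**Conclusion.** The point holds as a defect in a pre-specified contingency. A reader might infer that pairing a random subject effect with an unstructured matrix itself makes the Week 6 result wrong. It does not: the marginal covariance, estimate and standard error are unchanged, and the only route to harm is a failure that activates the fallback.

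If the fallback is used and visit variances differ, the primary standard error is wrong. It is too small when Week 6 variance exceeds the three-visit average, too large when it is below it, and almost right when the SD changes steadily through Week 6. Over the assumed SDs, per-comparison type I error at nominal 5% runs from 2.1% to 8.8%. These figures illustrate what could happen; they are not predictions, since the documents give no SDs for Weeks 2 and 12. The open choice among three structures is a weakness whatever the variances turn out to be. It merits correction because the test is confirmatory and the correction is cheap.

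**What to change.** In SAP 7.6.3, remove the random-effect sentence and state that the unstructured matrix is the within-subject residual covariance, with subject as the unit and no separate random subject effect. Check that the code matches.

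Replace the fallback with a fixed sequence, taking the first structure that converges: for example heterogeneous Toeplitz, then heterogeneous AR(1), then heterogeneous compound symmetry. Use an empirical (sandwich) standard error for any of them, and name the degrees-of-freedom method if the code does not already do so. Drop variance components without a subject effect.

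The cost is a few lines of SAP text and code, with no effect on patients or data collection. Two limits remain. Heterogeneous Toeplitz has 5 parameters against 6 for the unstructured matrix, so the first step is only a small simplification. Heterogeneous Toeplitz and heterogeneous AR(1) also still give the 4-week and 6-week gaps the same correlation; the sandwich estimator covers this for the standard error.
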